**Figure 1: Treatment Group Sequence**

All neonates enrolled will receive daily doses of blinded study treatment through 34 weeks of post-conceptual age or neonatal intensive care unit (NICU) discharge, whichever comes first. While in the NICU, neonates will be evaluated daily for signs/symptoms of NEC, feeding volumes/feeding tolerance, AEs, and concomitant medications. Physical examinations and vital signs will be performed daily during the dosing period and at the end of dosing/NICU discharge. Growth assessments will be performed every other week while in the NICU and at the end of dosing/NICU discharge. Assessments for complications of prematurity, including retinopathy of prematurity (ROP), intraventricular hemorrhage (IVH), and bronchopulmonary dysplasia (BPD) will be

performed at protocol defined timeframes (see [Section 11.2](#)). Neonates enrolled in the study will have fecal/meconium samples collected daily through 4 days following the start of dosing and weekly thereafter until NICU discharge to determine fecal shedding of [REDACTED] (STP6) and [REDACTED] (STP11).

Following completion of blinded study treatment dosing, neonates will be evaluated at 1 week, 1 month, 3 months, and 6 months for safety and growth assessments.

### 7.1.1. Stopping Criteria

The following stopping events reported to Leadiant will be evaluated by the DSMC to assess whether the events merit a temporary suspension or stopping study enrollment:

- Any death due to an AE assessed to be directly related to the administration of STP206
- Isolation of an STP206 organism from a normally sterile site (including bacteremia but excluding peritonitis in association with intestinal necrosis) in any subject

All reports of stopping events will be forwarded to the DSMC for review. If either of the above events occurs, enrollment will be suspended temporarily while the DSMC is evaluating the event. Subjects on blinded study drug will continue dosing during the assessment of the event.

If a stopping criterion is met, the DSMC will perform an unblinded review of the event to assess causality and its overall impact on subject safety and provide its recommendations to Leadiant. If an event, in the opinion of the DSMC, is related to the administration of STP206, dosing of all ongoing study subjects will be halted, and the study will be suspended temporarily. FDA will be notified of all DSMC's recommendations before taking any actions with the study.

A flow diagram for the process of evaluating infections of normally sterile sites that are suspected to be associated with STP206 organisms (*i.e.*, gram positive bacilli) is provided in [Appendix E](#).

### 7.1.2. Study Periods

Subject participation will be classified into four study periods:

- Screening Period – from the time of informed consent through administration of the first dose of study drug.
- Treatment Period – this will be the period when subjects are actively being administered blinded study treatment.
- Immediate Follow-up Period – this period will begin the day following the last dose of blinded study treatment through 30 days following administration of the last dose.
- Long-Term Follow-up Period – this period will begin after completion of the immediate follow-up period.

### 7.1.3. Recruitment and Enrollment

The total duration of recruitment for the study will be approximately 4 years.

### 7.1.3.1. Recruitment Definitions

- Screen Failure - Neonates for whom parental informed consent is obtained and do not proceed to study treatment (e.g., withdrawal of parental consent, does not meet entry criteria). Screening data will be documented in the study specific Screening Log. Reasons for screen failure will be documented in the subject's source documents and in the Screening Log.
- Enrolled – Neonates who pass all screening evaluations and are randomized to blinded study treatment.
- Treated – Neonates who are enrolled and receive at least one dose of blinded study treatment.
- Treatment Discontinuation – Neonates who receive blinded study treatment but fail to complete treatment through 34 weeks of post-conceptual age or hospital discharge.
- Study Discontinuation – Neonates who complete blinded study treatment but not all follow-up visits
- Completed Subject - Neonates who complete treatment and all follow-up visits

## 7.2. Study Treatments

### 7.2.1. Rationale for Dose Selection and Choice of Control Groups

The STP206 doses and treatment duration selected for this study are based upon studies [REDACTED] evaluating [REDACTED]

[REDACTED] The doses planned for this study (total of  $1.1 \times 10^9$  CFU for low dose and  $9.9 \times 10^9$  CFU for high dose) bracket the average dose administered in these studies.

[REDACTED]

[REDACTED]	[REDACTED]	[REDACTED]	[REDACTED]	[REDACTED]
[REDACTED]	[REDACTED]	[REDACTED]	[REDACTED]	[REDACTED]
[REDACTED]	[REDACTED]	[REDACTED]	[REDACTED]	[REDACTED]
[REDACTED]	[REDACTED]	[REDACTED]	[REDACTED]	[REDACTED]
[REDACTED]	[REDACTED]	[REDACTED]	[REDACTED]	[REDACTED]
[REDACTED]	[REDACTED]	[REDACTED]	[REDACTED]	[REDACTED]
[REDACTED]	[REDACTED]	[REDACTED]	[REDACTED]	[REDACTED]
[REDACTED]	[REDACTED]	[REDACTED]	[REDACTED]	[REDACTED]
[REDACTED]	[REDACTED]	[REDACTED]	[REDACTED]	[REDACTED]
[REDACTED]	[REDACTED]	[REDACTED]	[REDACTED]	[REDACTED]

[REDACTED]

[REDACTED]

The dosing duration planned for this study (through 34 weeks of post-conceptual age or hospital discharge, whichever comes first) is consistent with the dosing durations employed in these studies. The dosing duration is also supported by the knowledge that neonates will be at minimal risk of NEC and will be discharged at a post-conceptual age of 34 weeks.

The control group (standard of care plus STP206 reconstitution vehicle) will provide a comparison of incidence of clinical events and study endpoints in a blinded fashion and minimize bias.

### 7.3. Assignment of Subjects to Treatment

Neonates enrolled into the study will be randomized to receive either STP206 or control in a 2:1 ratio based upon a pre-prepared, computer generated, centralized randomization schedule.

To assure a balance in birth weight among treatment groups, randomization will be stratified by birth weight.

After obtaining informed consent and completion of screening assessments, neonates passing screening will be eligible for enrollment. The unblinded site research pharmacist (or other designated site personnel who has no role in screening, enrolling or qualifying study subjects) will obtain a randomization number and treatment assignment through an automated randomization system.

The unblinded research pharmacist is responsible for maintaining treatment assignments in a secure place with restricted access to assure the integrity of the study blind and prevent the identity of treatment assignments from becoming known to blinded staff at the research facility.

## **7.4. Study Duration**

The total duration of the study will be approximately 55 months.

### **7.4.1. Duration of Treatment and Subject Participation**

Subjects enrolled in this study will receive a variable number of daily doses of STP206 or vehicle based on their gestational age. Based on the study entry criteria, treatment will be between 2 and 11 weeks in duration determined by the subject gestational age at birth. All neonates will be followed the 6-month postdosing visit.

The total duration of study participation for each study subject will be between 28 and 39 weeks.

## **7.5. Methods Used to Minimize Bias**

Eligible study subjects for whom parental consent is obtained will be consecutively enrolled and randomized to receive STP206 or control using a centralized randomization system (see [Section 7.3](#)) in an effort to minimize subject selection bias.

All staff performing study assessments will be blinded to the identity of the treatment assignment to which the infant has been randomized in an effort to minimize bias in study assessments. Fecal shedding results will not be shared with the study sites during the course of the study as these results may potentially unblind study staff to the identity of treatment.

As study drug is supplied in open-label fashion, the study will require unblinded site personnel to randomize subjects and prepare study drugs for administration. The study will use a third party (e.g., pharmacist or other designated site personnel who has no role in screening, enrolling, or qualifying study subjects) blind to minimize bias in study conduct.

As there may be a visual difference between STP206 and control treatments (white vs. clear, respectively), an opaque syringe will be used to administer the blinded study treatment.

## **7.6. Appropriateness of Study Measurements**

The physical examinations and AE assessments used in this study are standard measures of monitoring safety during the course of clinical trials. The assessments and monitoring used to diagnose NEC and complications of prematurity are standard methods utilized in NICUs and are appropriate to assess study objectives. Growth measurements used in this study are standard for the determining neonatal growth.

Fecal shedding will be monitored by validated qPCR assays developed specifically for the detection of the STP206 organisms in feces.

Identification of STP206 organisms in cultures of normally sterile sites will be assessed using validated qPCR assays that were developed for the detection of the components of STP206 from isolates.

## 7.7. Study Monitoring Committees

An independent DSMC will be used to review data generated in this study, provided as a separate document. A [Charter](#) for the DSMC outlining the membership, roles and responsibilities was developed and finalized prior to the initiation of the study and submitted to the FDA on 03 December 2013 (SN 0030).

Available data on primary and secondary endpoints, including AEs, will be included in each review. The DSMC can give recommendations regarding continuation of study, temporary hold on study while additional data is further analyzed, or termination of the study. The DSMC will also review events that may constitute stopping criteria (see [Section 7.1.1](#)) on an as needed basis. Unscheduled DSMC review of study data may occur at any time on an as-needed basis if requested by the DSMC.

The DSMC will review data for each dose/birth weight group to assess whether proceeding to lower birth weight and/or higher STP206 doses is warranted. Data reviewed at each DSMC meeting will follow the following schedule:

- For the first group of subjects (Study Group 1a – Birth weight 2000 to 1501 g and low dose STP206), data will be reviewed through the completion of dosing.
- For the next six DSMC reviews (Study Groups 1b through 4a), data the current dose group will be reviewed through the completion of dosing along with 30-day post dosing data from the prior dose group.
- For the final DSMC review (Study Group 4b), data through 30-days post dosing will be reviewed.

## 8. STUDY DRUG AND TREATMENTS

### 8.1. Description of Study Drug(s)

#### 8.1.1. STP206

STP206 Live Biotherapeutic is a combination of defined quantities of lyophilized [REDACTED] (STP6) and [REDACTED] (STP11) components of drug product. The product components will be individually reconstituted with water for injection (USP) prior to administration.

#### 8.1.2. Control

The control for this study will be water for injection (USP), the vehicle used to reconstitute STP206.

### 8.2. Supply and Labeling

#### 8.2.1. How Supplied

##### 8.2.1.1. *STP206*

The individual components of STP206, [REDACTED] (STP6) and [REDACTED] (STP11), will be supplied separately in individual 3-mL-glass vials covered with rubber stoppers and aluminum caps with color-coded plastic flip-tops.

- Each vial of STP6 contains between  $5 \times 10^8$  and  $5 \times 10^{10}$  CFU per vial and identified with a white flip-top.
- Each vial of STP11 contains between  $5 \times 10^7$  and  $5 \times 10^9$  CFU per vial and identified with a violet flip-top.

STP6 and STP11 components of STP206 drug product will be packaged in the separate boxes containing 50 vials per box.

[figure not shown]
[figure not shown]
### 8.2.1.2. *Control / Vehicle*

Control/vehicle, *i.e.*, water for injection (USP), will not be supplied by Leadiant; it will be provided by the research sites conducting the study.

### 8.2.2. Labeling

Each vial of the STP206 drug product will be labeled with the product component name and a viable cell (CFU) count per vial, Investigational use statement, and a statement cautioning the product is only for oral use. The vial label will also have extra space for recording of dispensing date and ID of the subject to whom the drug was administered. The samples of vial labels are provided in [Figure 2](#).

**Figure 2: Sample of STP6 and STP11 Vial Labels**

Each box of ██████████ (STP6) and ██████████ (STP11) will be labeled with the box number, protocol number, product name, lot number, manufacture date, Investigational use statement, storage condition, preparation and administration instructions and manufacturer and sponsor information. The samples of box labels are provided in [Figure 3](#).

**Figure 3: The Box Label Samples for Components of STP206 Drug Product**

Sample Label	
Box # [XX]	
Protocol STP206-002	***FOR ORAL USE ONLY***
Contains 50 vials of [REDACTED]	STP6 (5 x 10  to 5 x 10  cfu/vial)
Lot No. 08SBF03	Date of Mfg.: 07Nov2008
	Store at 2 – 8 °C
Caution: New Drug - Limited by Federal Law to Investigational Use	
Reconstitute with Water for Injection and co-administer with [REDACTED] STP11 per protocol instructions	
Manufactured by:	[REDACTED]
Manufactured for:	Leadiant Biosciences, Inc. [name] [contact]

Sample Label	
Box # [XX]	
Protocol STP206-002	***FOR ORAL USE ONLY***
Contains 50 vials of [REDACTED]	STP11 (5 x 10  to 5 x 10  cfu/vial)
Lot No. 09SLF01	Date of Mfg.: 12Mar2009
	Store at 2 – 8 °C
Caution: New Drug - Limited by Federal Law to Investigational Use	
Reconstitute with Water for Injection and co-administer with [REDACTED] STP6 per protocol instructions	
Manufactured by:	[REDACTED]
Manufactured for:	Leadiant Biosciences, Inc. [name] [contact]

### 8.3. Storage Conditions

#### 8.3.1. STP206

The vials of individual components of STP206, [REDACTED] (STP6) and [REDACTED] [REDACTED] (STP11) will be stored under monitored refrigerated conditions (2 - 8°C) prior to reconstitution for use in the research pharmacy at each site.

---

---

## 8.4. Preparation for Administration

### 8.4.1. STP206

Each vial of STP6 [REDACTED] and STP11 [REDACTED] will be reconstituted using with 1.0 mL of water for injection of USP quality in the research pharmacy (Note: STP206 must not be reconstituted at the subject's bedside). The appropriate volume of the reconstituted bacterial suspension will be removed from STP6 and STP11 vials by sterile syringes and stored in the individual syringes until administered. The reconstituted STP206 must be administered within 2 hours following reconstitution.

The following dose volumes will be administered:

- For the low dose of STP206, 0.1 mL of STP6 and 0.1 mL STP11 will be drawn up for administration (0.2 mL total).
- For the high dose of STP206, 0.9 mL of STP6 and 0.9 mL of STP11 will be drawn up for administration (1.8 mL total).

The syringes with the reconstituted STP206 will be labeled with the protocol number, subject identification (randomization number and initials), date and time of preparation, dose volume, and the words "contains STP6 or vehicle" [REDACTED] or "contains STP11 or vehicle" [REDACTED].

### 8.4.2. Control

Syringes containing the matching volume of vehicle for both STP6 and STP11 will be used as the control. Syringes will be labeled in the same manner as syringes with STP206 to maintain study blinding.

## 8.5. Study Drug Accountability

The Food and Drug Administration requires accounting for the disposition of all study material (active or control). The Investigator is responsible for ensuring that a current record of study drug disposition is maintained and dispensed only at an official study site by authorized personnel as required by applicable regulations and guidelines. Records of product disposition as required by federal law consist of the date received, date dispensed/administered, quantity dispensed/administered, and the subject to whom the material was administered.

The Investigator or designee authorized by the Investigator will be responsible for maintaining accurate records of the shipment, dispensing/return of the study drug by the study site, and return of used/undispensed study drug to Leadiant. Drug accountability records must be available for inspection by Leadiant or its representative and is subject to inspection by a regulatory agency (*e.g.*, FDA, EMA) at any time. Copies of the records will be provided to Leadiant at the conclusion of the study.

At the termination of the study, all unused investigational product must be returned to Leadiant (or destroyed, if not feasible to return to Leadiant). A written explanation will be required for any product not returned to Leadiant, stating the reason it was not returned. An Investigational Product Return Form and the study drug accountability form must be maintained in either the pharmacy or

study site. Study drug accountability records will be reviewed by an unblinded monitor on a routine basis.

## **9. STUDY POPULATION**

### **9.1. Number of Subjects**

The study will be conducted at up to 20 active centers.

This study will require at least nine evaluable neonates (*i.e.*, completing minimum dosing duration described in [Section 11.3.2](#) and having a post-dosing assessment performed) per treatment group for each of the eight treatment groups. It is not expected that there will be a high percentage of neonates that do not meet evaluability criteria. Thus, to achieve the required number of evaluable neonates, it is anticipated that approximately 100 to 110 neonates will be enrolled in this study.

There are no limitations on the number of subjects that may be enrolled at each center.

### **9.2. Inclusion Criteria**

1. Neonates with birth weights between 2000-500g
2. Ability to start treatment within four (4) days after birth.
3. Gestational age between 23 and 32 weeks at birth.
4. Obtaining of informed consent from the subject's appropriate legally authorized representative(s) (e.g., one or both parents, legal guardian), as defined by local law and IRB/IEC requirements, after those individuals have been provided with a full understanding of the study purpose and procedures.
5. Parent(s) who agree to allow the Principal Investigator and his/her staff to follow the procedures and assessments required by the protocol.

### **9.3. Exclusion Criteria**

1. Infants with, or at high probability for, early onset sepsis (positive blood cultures or with the expectation of empirical antimicrobial therapy for  $\geq 5$  days).
2. Infants with persistent pulmonary hypertension of the newborn (PPHN)
3. Congenital chromosomal anomalies.
4. Congenital or acquired gastrointestinal pathology that preclude feeds within 7 days after birth (e.g., cleft lip is not an exclusion criterion, but a duodenal atresia is).
5. Infants in extremis to whom no further intensive care is offered by attending neonatologist (e.g., infant being provided only hospice/comfort care).
6. Other conditions of the infant, which in the opinion of the attending neonatologist, preclude participation.
7. Positive maternal HIV status.
8. Participation in another interventional clinical trial.

9. Small for gestational age neonates, i.e. neonates that weigh less than the 10th percentile for their gestational age according to the Estimated Fetal Weight Percentile Chart in [Appendix D](#).

#### **9.4. Post-Enrollment Restrictions**

##### **9.4.1. Concomitant Medications**

Products containing probiotic bacteria are prohibited. There are no other restrictions on concomitant medications.

##### **9.4.2. Concurrent Treatments**

There are no restrictions on concurrent treatments other than those described under clinical management ([Section 10.6](#)).

##### **9.4.3. Dietary Restrictions**

Dietary management of neonates is described in [Section 10.6.1](#).

#### **9.5. Withdrawal of Enrolled Subjects**

In the absence of a medical contraindication or significant protocol violation, every effort will be made by the Principal Investigator to keep subject in the study. The primary reason for a subject withdrawing prematurely should be selected from the following standard categories:

- Adverse Event - clinical or laboratory events that in the judgment of the Principal Investigator require discontinuation of study medication in the best interests of the subject.
- Death – death of the subject, whether study related or not.
- Withdrawal of Consent – subject’s parents desire the subject to be withdrawn from further participation in the study in the absence of a medical need to withdraw determined by the Principal Investigator.
- Lost to follow-up - the subject did not return for follow-up visit(s) following the completion of study treatment and hospital discharge despite attempts to contact the subject’s parents to maintain scheduled appointments.
- Protocol Non-compliance - the subject’s participation in the study failed to meet protocol requirements, which had a direct impact on subject safety and evaluability of the subject’s data. The violation necessitated premature termination from the study.
- Subject meets withdrawal criteria – the subject’s condition meets the criteria for withdrawal from the study ([Section 9.5.1](#)).
- Other - causes of premature termination from the study other than the above (e.g., termination of study by Leadiant, subject relocated).

##### **9.5.1. Withdrawal Criteria**

Subjects will be withdrawn from the study if the subject meets any of the following criteria after the initiation of study treatment:

- Necrotizing enterocolitis (Bell stage II or worse)

- Any event requiring stopping of all enteral intake for more than 7 days

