### 9.5.2. Withdrawal Procedures

All subjects who are withdrawn from the study will have a post dosing assessment completed. All subjects who received blinded study treatment, with the exception of those for whom consent is withdrawn, will be followed for all subsequent study assessments per study protocol.

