## 10.5.2. Relevant Neonatal Morbidities/Complications of Prematurity

### 10.5.2.1. *Necrotizing Enterocolitis*

Necrotizing Enterocolitis, (see [Appendix B](#) for diagnostic and staging criteria) will be assessed through physical findings (abdominal distension & tenderness) and feeding tolerance. If NEC is suspected, an abdominal X-ray will be obtained to determine the presence of pneumatosis intestinalis, portal venous air, or free air.

If NEC is diagnosed, study drug administration will be discontinued immediately.

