### 10.8.2. Suspension of Study Drug Administration

Study drug administration will be suspended temporarily in subjects with a case of suspected sepsis (see [Section 10.3.5.1](#)) or infection of a normally sterile site (see [Section 10.3.5.2](#)). Study drug may be re-initiated at the discretion of the Investigator, if the subject's clinical condition permits and:

- Cultures are negative for gram positive bacilli or,

- STP-206 organisms are not confirmed by central laboratory analysis.

Additionally, dosing of blinded study treatment may be withheld at the discretion of the physician Investigator. The reason for suspension of blinded study treatment will be documented in the subject's source documents and the case report form.

Neonates will be discontinued from the study if:

- Dosing is suspended for greater than seven consecutive days or
- More than two suspensions of oral dosing of five or more consecutive days each in duration are required.

If the neonate is placed on NPO status for suspected NEC and the NPO status is maintained for greater than 24 hours, dosing of blinded study drug will be suspended until NPO status is removed.

If NEC is diagnosed, study drug administration will be immediately discontinued.

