## **11.2. Assessment Schedule for Complications of Prematurity**

### **11.2.1. Necrotizing Enterocolitis (NEC)**

Assessments of signs and symptoms of NEC will be performed daily while the neonate is hospitalized. If NEC is suspected, abdominal X-rays will be performed (see [Appendix B](#)).

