## **11.3. Dosing Period**

### **11.3.1. Daily Assessments During Dosing**

During the dosing period, the following assessments will be performed daily:

- Physical Examination and vital signs
- Assessments of signs and symptoms of NEC
- Assessment of AEs
- Assessment of concomitant medication changes
- Assessment of feeding volumes and tolerance

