### **11.4. Early Withdrawal Study Assessments**

For subjects who withdrawal from the study prior to the 6-month post-dosing follow-up, the following procedures will be performed:

- Physical Examination
- Vital Signs
- Growth Assessment
- Assessment of AEs
- Assessment of concomitant medication changes

For subjects who withdrawal from the study prior to the 6-month follow-up assessment, the following procedures will be performed:

- Growth Assessment

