Post Dosing 6 Month ^d	181 to 195 days	181 <= (assessment date – expected last dose date+1) <= 195 days
Post Dosing 18 Month/End ^d	Not specified	520 <= (assessment date – expected last dose date+1) <= 576 days
Withdrawal Prior to Post Dosing 6 Month ^d	Not specified	assessment date >= date of withdrawal and (assessment date – expected last dose date+1) <= 181 days
Withdrawal between Post Dosing 6 and 18 Month ^d	Not specified	assessment date >= date of withdrawal and 196 days < (assessment date – expected last dose date+1) < 520 days

- a- Windows for vital sign measurements and physical examinations.
- b- Window for fecal sample.
- c- Window for IVH measurement.
- d- Windows for growth assessment (note that Post Dosing 18 Month data will only be presented in listings).
- e- Windows for Post Dosing may be adjusted to account for patients that terminated dosing early. For example, if a subject early terminates dosing at Week 10 but was expected to complete dosing at Week 11, then the Post Dosing window will be adjusted to reflect planned time point after expected dosing completion.

If a subject has more than 1 assessment occurring in the same visit window, the data from the visit closest to the scheduled study day will be used for summaries. If two assessments have the same distance from the scheduled study day, the assessment after the scheduled study day will be used for the analyses.

If multiple assessments occur as Baseline (screening or Day 1 prior to dosing), then the last assessment before the first study dose will be used for the analyses.

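### Protocol 9.5.1, 10.8.2 and 11.4 word a stop for NEC or long suspension as leaving the study, while 9.5.2 keeps these infants in follow-up

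*Protocol*

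**What the plan says.** **Leaving the study.** Protocol 9.5.1 opens with "Subjects will be withdrawn from the study if the subject meets any of the following criteria after the initiation of study treatment" and lists NEC of Bell stage II or worse and any event that stops all enteral intake for more than 7 days. Protocol 10.8.2 has "Neonates will be discontinued from the study if", followed by one suspension longer than seven consecutive days, or more than two suspensions of at least five days each.

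**Stopping the drug only.** Protocol 10.5.2.1 says "If NEC is diagnosed, study drug administration will be discontinued immediately" and does not mention leaving the study. Section 10.5.1.1 and the end of 10.8.2 do the same.

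**Follow-up.** Protocol 9.5.2 requires a post-dosing assessment for withdrawn subjects and says that treated subjects, "with the exception of those for whom consent is withdrawn, will be followed for all subsequent study assessments per study protocol". Protocol 11.4 gives two procedure lists for infants who leave before 6 months. The first has five items, including adverse events. The second, introduced by "For subjects who withdrawal from the study prior to the 6-month follow-up assessment, the following procedures will be performed", has growth only.

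**In-hospital checks.** The clinical-event endpoint in 6.3.2 runs to hospital discharge. Section 11.3.1 lists NEC, feeding, adverse event and medication checks under "During the dosing period, the following assessments will be performed daily". Section 7.1 ties them to the NICU stay. For NEC alone, 11.2.1 says "Assessments of signs and symptoms of NEC will be performed daily while the neonate is hospitalized".

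**SAP.** In 6.2.2, Table 4, the row for withdrawal before the 6-month visit takes assessments meeting "assessment date >= date of withdrawal and" a day count of at most 181 from the expected last dose.

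**The concern.** An infant cannot both leave the study and complete its remaining assessments. The infants concerned have had definite NEC, prolonged loss of enteral intake or long dosing gaps, so their later deaths, serious events and growth matter most in a trial whose primary objective is safety. A coordinator stopping an infant is likely to open 10.8.2 or 11.4, and neither refers to 9.5.2. If the infant is closed out after one visit, the 1-week, 1-, 3- and 6-month data are reduced to a single assessment. If daily checks end with dosing, feeding intolerance and other events before discharge may go unrecorded although the endpoint covers them. In the growth tables, an infant who is properly followed could be counted at a scheduled visit, as an early withdrawal, or both.

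**Working it through.** The plan gives no figure to reproduce on this point, and the sample size is stated not to be statistically based. The check is mainly a comparison of text.

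**1. Does any section settle the status of these infants?**

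| Source | What it implies after a stop for NEC or long suspension |
|---|---|
| Protocol 9.5.1, 10.8.2 | Out of the study |
| Protocol 10.5.1.1, 10.5.2.1, end of 10.8.2 (NEC) | Off the drug; study status not mentioned |
| Protocol 11.4 | One early-withdrawal visit for those out of the study |
| Protocol 9.5.2 | All later assessments, unless consent is withdrawn |
| Protocol 10.3.5, 12.1 | Adverse events collected to 6 months after the last dose |
| SAP Table 4, note e | Post-dosing windows kept for infants who ended dosing early |

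The last three rows agree on continued follow-up. The first and third do not, and 10.8.2 and 11.4 carry no link to 9.5.2.

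The definitions in 7.1.3.1 do not resolve this. Study Discontinuation requires that treatment was completed, so an infant removed under 9.5.1 or 10.8.2 before completing treatment cannot meet it. Only Treatment Discontinuation fits. Yet SAP 8.1 tabulates discontinuation from the study with reasons.

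**2. How far do in-hospital checks extend?** The endpoint runs to hospital discharge. Daily NEC checks also extend through hospitalization (11.2.1). Daily feeding and adverse event checks are tied to dosing (11.3.1) or to the NICU stay (7.1). Section 10.5.1 asks for daily feeding records but gives no end point. No passage says that daily feeding and adverse event checks continue to discharge after dosing stops.

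**3. SAP Table 4.** Counting days as assessment date minus expected last dose date plus 1:

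- 1 week: 6–13
- 1 month: 21–35
- 3 months: 85–99
- 6 months: 181–195
- Withdrawal before 6 months: on or after withdrawal, up to 181

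For an infant withdrawn during dosing and then followed, the first three windows lie wholly inside the withdrawal row. The 6-month window touches it only at day 181. The withdrawal row has no target day, so the closest-visit rule cannot be applied within it, and no rule ranks it against the scheduled rows. Footnote d confines it to growth, and SAP 8.7.4 reports early withdrawal as a separate growth time point.

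**4. Scale.** Inputs are 12 infants per group and 2:1 allocation (Protocol 7.1), and a background NEC rate of about 10% in VLBW infants (Protocol 5.1).

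- Infants at or below 1500 g: 3 strata × 2 dose groups × 12 = 72 of 96 planned.
- Expected NEC cases: 72 × 0.10 = 7.2. At an assumed 5% or 15%: 72 × 0.05 = 3.6 and 72 × 0.15 = 10.8.
- Chance of at least one case at 10%: 1 − 0.9^72 = 0.999 across the 72, and 1 − 0.9^12 = 0.72 in one group of 12.
- Weight of one event: 1/8 = 12.5 points among the STP206 infants of one group, and 1/4 = 25 points among its controls.
- Pooled over strata: each dose has 4 × 8 = 32 and control has 8 × 4 = 32, so 1/32 = 3.1 points.

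**The case against.** The best defence is that 9.5.2 directly follows 9.5.1, is written for withdrawn subjects, and excepts only withdrawal of consent. With the 6-month adverse event period, section 9.5 gives one answer: follow the infant. That stands. A reader might infer that the protocol leaves follow-up open, or that data after a stop depend wholly on which section a site chooses. The text does not support so much. What survives is that 10.8.2 and 11.4, used alone, lead elsewhere.

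Other stronger readings also fail:

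- **That the SAP treats these infants as gone.** Note e to Table 4 plans for them, and the scheduled rows do not exclude them. The SAP carries both readings.
- **That the withdrawal row absorbs all later visits.** It ends at day 181, and earlier visits also satisfy their own rows. The defect is overlap, in growth only. Deaths and adverse event tables are not assigned through this row.
- **That the two lists in 11.4 contradict each other.** Growth is in both, so the longer list satisfies the shorter. The post-dosing schedule shows one early-withdrawal column with all five procedures.
- **That daily checks must stop with dosing.** Section 11.3.1 says what is done during dosing and does not say that checks then end. It can be read cumulatively with 7.1 and 11.2.1. The gap is the absence of an explicit end at discharge. The dosing-period schedule table could not be read in the public copy, so nothing is inferred from it.

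It is also fair that comparisons are exploratory, that combined-strata displays dilute a single event, and that the 10% rate is background incidence not split by Bell stage, whereas 9.5.1 begins at stage II.

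**Conclusion.** The inconsistency is in the current text and should be corrected. The intended rule is most likely continued follow-up, but it is contradicted by 9.5.1, 10.8.2 and 11.4 and not rescued by the definitions in 7.1.3.1. The end of in-hospital recording and the overlapping SAP growth row are smaller, related gaps.

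About 7 of 72 infants would be affected through NEC if the background rate applied (3.6 to 10.8 at an assumed 5–15%). The stage II subset may be smaller. The documents give no rate for long suspensions or prolonged loss of enteral intake, so the total is unknown. One missed event would matter in a single group and much less in the pooled display.

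A reader might go on to infer that events were lost, or that a harmful dose would look safer because its arm stops dosing more often. The documents show neither. SAP 8.7.2 notes that some sites used a different 6-month anchor. That makes varied reading of follow-up rules plausible, but it does not show that any withdrawn infant was lost.

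**What to change.** Leave every trigger for stopping unchanged and reconcile the surrounding text with 9.5.2:

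- In 9.5.1 and 10.8.2, describe these infants as discontinued from study treatment and remaining in the study under 9.5.2.
- In 7.1.3.1, define the end of study participation separately from the end of treatment, so that infants with incomplete treatment can be classified.
- In 11.3.1, state that NEC, feeding, adverse event and concomitant-medication data are recorded until hospital discharge whatever the dosing status.
- In 11.4, limit the visit to infants who actually leave follow-up, refer to 9.5.2, and use the single procedure list in the schedule.
- In SAP Table 4, define the withdrawal date as the end of study participation and restrict that row to the final assessment of those infants.

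The cost is wording in a protocol amendment and one SAP table row. The post-dosing visits are already scheduled. The downside is a little more CRF entry for infants still in hospital after dosing stops.
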